### **7.2 NULL AND ALTERNATIVE HYPOTHESES**

The superiority of treatment with BI 1026706 to placebo will be tested for CSFT change from baseline at week 12 by a pairwise comparison against placebo at the  $\alpha=0.05$  level. The population used will be the Full Analysis Set (FAS).

Let  $M_{HA}$  be the mean change from baseline in CSFT ( $\mu\text{m}$ ) after 12 weeks in BI 1026706 group.

Let  $M_{HB}$  be the mean change from baseline in CSFT ( $\mu\text{m}$ ) after 12 weeks in placebo group

The primary objective hypothesis is:

$$H_0: M_{HA} - M_{HB} = 0$$

$$H_1: M_{HA} - M_{HB} \neq 0$$

The test of the null hypothesis will be supported by the 95% confidence interval (CI) for  $M_{HA} - M_{HB}$  and the null hypothesis will be rejected if the CI excludes 0  $\mu\text{m}$ .

### **7.3 PLANNED ANALYSES**

The statistical analysis will be based on the following populations:

Treated Set (TS)

The TS will consist of all patients who were treated with at least one dose of study drug (BI 1026706 or placebo).

#### Full Analysis Set (FAS)

The FAS will consist of all patients who were randomised, treated with at least one dose of BI 1026706/placebo and provided baseline and at least one post-randomization CSFT measurement.

#### Pharmacokinetic analysis Set (PKS)

The PKS will consist of all patients in the TS for whom at least one evaluable BI 1026706 plasma concentration is available.

### 7.3.1 Primary endpoint analyses

The primary analysis of the primary endpoint, change from baseline in CSFT at 12 weeks, will be performed on the FAS. Therefore, all randomised patients who were treated with at least one dose of BI 1026706/placebo, had a baseline and at least one on-treatment CSFT measurement will be included.

Comparisons between treatment groups for the primary endpoint will be based on a mixed effect repeated measures model (MMRM). This model will include treatment, previous DME treatment, week and treatment by week interaction as fixed categorical effects. Also, baseline CSFT and baseline CSFT by week interaction as continuous fixed effects. An unstructured covariance matrix will be used to model the within-patient variation. The SAS procedure MIXED will be used involving the REML and the Kenward-Roger approximation for denominator degrees of freedom. This approach is described in Kenward and Roger ([R10-4391](#)). Adjusted mean values as well as treatment contrasts will be presented together with the 95% CIs and p-values.

The statistical model will be:

CSFT change from baseline = overall mean + continuous baseline CSFT + previous DME treatment + treatment + week + baseline CSFT by week interaction + treatment by week interaction + random error

Baseline CSFT will be defined as the last available CSFT measurement obtained before randomization.

Data obtained after the start of rescue medication will not be used in the primary analysis of the primary endpoint.

### 7.3.2 Secondary endpoint analyses

See [Section 7.3.4](#).

#### 7.3.4 Safety analyses

AEs will be coded using the Medical Dictionary for Regulatory Activities (MedDRA) coding dictionary. Standard BI summary tables and listings will be produced. All AEs with an onset between start of treatment and end of the REP (residual effect period), a period of 4 days after the last dose of trial medication, will be assigned to the treatment period for evaluation. All treated patients will be included in the safety analysis. In general, safety analyses will be descriptive in nature and will be based on BI standards. No hypothesis testing is planned.

Statistical analysis and reporting of AEs will concentrate on treatment-emergent AEs. To this end, all AEs occurring between start of treatment and end of the REP will be considered 'treatment-emergent'. The REP is defined as the time period after the last dose administration of trial medication when measurable drug levels or PD effects are still likely to be present. Adverse events that start before first drug intake and deteriorate under treatment will also be considered as 'treatment-emergent'.

Frequency, severity, and causal relationship of AEs will be tabulated by system organ class and preferred term after coding according to the current version of the Medical Dictionary for Drug Regulatory Activities (MedDRA).

Laboratory data will be analysed both quantitatively as well as qualitatively. The latter will be done via comparison of laboratory data to their reference ranges. Values outside the reference range as well as values defined as clinically relevant will be highlighted in the listings.

Clinically relevant ECG findings will be reported as AEs. Quantitative and qualitative ECG data from the ECG reading centre will be reported descriptively.

Treatment groups will be compared descriptively with regard to distribution of parameters as well as with regard to frequency and percentage of patients with abnormal values or clinically relevant abnormal values.

Vital signs, physical examinations, or other safety-relevant data observed at screening, baseline, during the course of the trial and at the end-of-trial evaluation will be assessed with regard to possible changes compared to findings before start of treatment.

[REDACTED]

[REDACTED]

[REDACTED]

[REDACTED]

[REDACTED]

[REDACTED]

#### 7.4 INTERIM ANALYSES

No interim analysis is planned.

#### 7.5 HANDLING OF MISSING DATA

For the primary analysis of the primary endpoint, if a patient misses a visit, the missing data will not be imputed and only on-treatment data will be included. The mixed effect model will handle missing data based on a likelihood method under the "missing at random assumption". Every randomised patient with at least baseline and one on-treatment measurement will be included in the analysis.

Additional details on the handling of missing data, including sensitivity analyses of the primary endpoint and [REDACTED], will be specified in the TSAP prior to unmasking. No imputation is planned for the analysis of AEs, laboratory data, and vital signs.

#### 7.6 RANDOMIZATION

Patients will be randomised in blocks to double-masked treatment. Approximately equal numbers of patients will be randomised to each treatment group. BI will arrange for the randomization and the packaging and labelling of study medication. The randomization list will be generated using a validated system, which involves a pseudo-random number generator so that the resulting treatment will be both reproducible and non-predictable. The block size will be documented in the CTR. Access to the codes will be controlled and documented.

#### 7.7 DETERMINATION OF SAMPLE SIZE

In the Diabetic Retinopathy Clinical Research Network study "Aflibercept, bevacizumab, or ranibizumab for diabetic macular edema" ([R15-5225](#)) the changes from baseline in CSFT at week 12 are estimated to be between 85 and 140  $\mu\text{m}$  for the aflibercept, bevacizumab and ranibizumab treatments. The common standard deviations as week 12 results are not presented. However, standard deviations were estimated from the confidence interval bars presented on the CSFT plots over time.

In order to achieve 80% power and with alpha at the 5% level for a two sided test, the number of patients required to detect a difference in the treatments is given in the table below for a range of mean differences in the treatments and common standard deviations.

Table 7.7: 1                      Sample Size

Mean difference [µm]	Common standard deviation [µm]	Number of patients per arm	Total sample size for the trial
20	20	14	28
30	20	7	14
40	20	5	10
20	30	29	58
30	30	14	28
40	30	8	16
20	40	51	102
30	40	23	46
40	40	14	28

It is assumed that the mean difference is 20 µm and the common standard deviation is 40 µm. Therefore a total sample size of 102 patients is assumed.

Calculations were performed using SAS® 9.3 proc power statistical package.

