### 3.3 SELECTION OF TRIAL POPULATION

A sufficient number of male and female patients with DM either type 1 or type 2 and center-involved DME with mild vision loss will be screened to ensure the randomization of 100 patients from around 44 study sites. The reason for conducting the study with many sites lies with the expected enrolment rate which might be low, as patients are only mildly affected and pure observation is a reasonable option before starting standard intravitreal injection therapy. To take account of the consistent evaluation of endpoints at all sites only prequalified study sites will participate, and SD-OCT images will be evaluated by an independent central reading center (CRC).

It is expected that around 2-3 patients will be randomised at each study site. If enrolment is delayed, additional sites may be recruited. Permission to enrol more than 15 patients per site must be obtained from the TCM at BI. This will only be allowed after a careful review of the enrolment status and of the site.

Screening of patients for this study is competitive across all countries within the study, i.e. screening for the study will stop at all sites when it is anticipated that a sufficient number of patients have been screened to yield the desired number of patients randomised to trial treatment. Investigators will be notified when sufficient patients have been screened and when screening is complete, and will not be allowed to recruit additional patients for the study. Patients who have completed Visit 1 procedures prior to notification of the termination of recruitment will be allowed to continue in the study, if they meet all entry criteria and they are able to follow the visit schedule specified in this Clinical Trial Protocol (CTP).

A screening log of all patients enrolled into the trial (i.e. who have signed informed consent) will be maintained in the ISF at the investigational site irrespective of whether they have been treated with investigational drug or not.

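### The sample-size table is labelled 80% power at two-sided 5%, but its numbers are too small: the chosen row needs 64 per arm, not 51, and the planned 50 per arm give about 70% power

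*Protocol*

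**What the plan says.** Protocol section 7.7 heads Table 7.7: 1 with "In order to achieve 80% power and with alpha at the 5% level for a two sided test, the number of patients required". The table gives patients per arm and in total for nine combinations of mean difference (20, 30, 40 µm) and common SD (20, 30, 40 µm). The section adopts 20 µm with SD 40 µm, for which the table shows 51 per arm, and concludes: "Therefore a total sample size of 102 patients is assumed". It names SAS PROC POWER but not the test option. The SDs come from a published anti-VEGF study, where "standard deviations were estimated from the confidence interval bars presented on the CSFT plots over time".

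Section 7.2 sets the primary test at alpha 0.05 with a not-equal alternative. It reports a 95% confidence interval, and the "null hypothesis will be rejected if the CI excludes 0".

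Section 7.3.1 analyses the endpoint with an MMRM that adjusts for previous DME treatment and for baseline: "Also, baseline CSFT and baseline CSFT by week interaction as continuous fixed effects".

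The planned size is stated differently elsewhere. In section 3.3 enough patients "will be screened to ensure the randomization of 100 patients from around 44 study sites", and the synopsis gives 100 in total, 50 per treatment. The SAP has no sample-size calculation of its own and refers the reader to the protocol.

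**The concern.** A difference of 20 µm with SD 40 µm is a standardised effect of 0.5. For two arms at two-sided 5% and 80% power this needs a little over 60 per arm, so 51 looks too small. The other rows show the same shortfall, which points to a wrong setting rather than a slip in one cell.

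The 80% figure is the only statement of sensitivity the protocol makes for its primary superiority test. If the true figure is nearer 70%, a null result would be read as carrying a 20% risk of having missed the assumed effect when the risk is about 30%.

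**Working it through.** **Inputs.** Two-sided alpha 0.05 (7.7, confirmed by 7.2); power 80%, difference d = 20 µm, common SD s = 40 µm (7.7); 1:1 allocation (4.1.4); 51 per arm (Table 7.7: 1) and 50 per arm (synopsis). Section 7.7 has no dropout allowance, so none is used here.

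**Method.** Two-sample t-test with n per arm: df = 2n − 2, noncentrality λ = d / (s·√(2/n)). Two-sided power is the probability that a noncentral t variable with these parameters falls outside ± the 97.5% point of the central t.

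**Chosen row (20 µm, SD 40 µm).**

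- n = 51: λ = 20 / (40·√(2/51)) = 2.525, df = 100, critical value 1.984; power 70.6%.
- n = 50: λ = 2.500, df = 98, critical value 1.984; power 69.7%.
- n = 63: power 79.5%. n = 64: λ = 2.828; power 80.1%.

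The requirement is therefore 64 per arm, 128 in total. The table is 13 per arm (26 in total) below it. The normal approximation gives n = 2·(40/20)²·(1.960 + 0.842)² = 62.8, so 63 per arm. The choice between t and z does not explain 51.

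**All rows**, t-test, n per arm:

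| Difference / SD (µm) | Table | Two-sided 5%, 80% | One-sided 5%, 80% | Two-sided 5%, 70% | Two-sided 5% power at table n |
|---|---|---|---|---|---|
| 20 / 20 | 14 | 17 | 14 | 14 | 72.1% |
| 30 / 20 | 7 | 9 | 7 | 7 | 73.1% |
| 40 / 20 | 5 | 6 | 4 | 5 | 79.1% |
| 20 / 30 | 29 | 37 | 29 | 29 | 70.4% |
| 30 / 30 | 14 | 17 | 14 | 14 | 72.1% |
| 40 / 30 | 8 | 10 | 8 | 9 | 69.9% |
| 20 / 40 | 51 | 64 | 51 | 51 | 70.6% |
| 30 / 40 | 23 | 29 | 23 | 23 | 70.1% |
| 40 / 40 | 14 | 17 | 14 | 14 | 72.1% |

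**Reproducing the plan's figures.** The labelled setting reproduces none of the nine rows. One-sided 5% at 80% power (the same n as two-sided 10%) reproduces eight, missing 40/20. Two-sided 5% at 70% power also reproduces eight, missing 40/30. A one-sided 5% unequal-variance (Satterthwaite) t-test, checked by simulation, fits all nine: for 40/20 it has about 78% power at n = 4 and 88% at n = 5. A one-sided setting is therefore the likeliest source, but this is an inference. The documents mention no one-sided test, 10% alpha or 70% power.

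**What 50 per arm supports at two-sided 5% and 80% power.** A true difference of 22.6 µm with SD 40 µm, or a residual SD of at most 35.3 µm with a 20 µm difference.

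**Effect of baseline adjustment.** If SD 40 µm is unadjusted and the covariate correlation is r, the residual SD is 40·√(1 − r²). The documents give no r, so these values are assumptions. At 50 per arm:

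| Assumed r | Residual SD (µm) | Power |
|---|---|---|
| 0 | 40.0 | 70% |
| 0.3 | 38.2 | 74% |
| 0.4 | 36.7 | 77% |
| 0.5 | 34.6 | 82% |

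Power reaches 80% at r of about 0.47 with 50 per arm, or 0.45 with 51.

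**The case against.** The best defence is that the trial may be adequately powered in practice. The chosen row is the most demanding cell of the grid. On the corrected values the other eight rows need at most 37 per arm, so 50 per arm is enough for all of them. The SD is approximate by the protocol's own account, and the MMRM adjusts for baseline CSFT, which could bring power to 80% if the correlation is about 0.47. The study is also an exploratory Phase IIa trial, where 70% power may be acceptable.

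These points limit the practical consequence but do not remove the error. Section 7.7 adopts the demanding row as its assumption. It does not invoke baseline adjustment or say whether SD 40 µm already reflects it, and adjustment cannot make a table defined by difference, SD, alpha and power come out right. An exploratory trial may choose 70% power, but should then report it as such.

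Two technical qualifications stand. That all nine rows fall short holds for the t-test; by the normal approximation 30/20 (needs 7) and 40/20 (needs 4) do not. By the t-test, 40/20 misses by only one patient per arm. Neither is the row the trial relies on.

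**Conclusion.** The concern holds. The label and the numbers in Table 7.7: 1 disagree, and section 7.2 supports the label, so the numbers must change. For the adopted assumption the requirement is 64 per arm, not 51, and the stated power is about 10 percentage points too high: 70.6% at 51 per arm and 69.7% at 50.

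These figures assume an unadjusted two-sample t-test with SD 40 µm and no loss of data. Section 7.7 allows for no dropout, section 3.3.4.1 does not replace withdrawals, and section 7.3.1 drops data after rescue, so losses would lower power. Baseline adjustment could raise it by an amount the documents do not give.

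The split between 102 in section 7.7 and 100 in the synopsis and section 3.3 is a separate, minor inconsistency worth 0.9 percentage points of power (70.6% − 69.7%). Type I error and the planned analysis are unaffected.

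**What to change.** In protocol section 7.7:

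- Replace the per-arm column of Table 7.7: 1, in its present row order, with 17, 9, 6, 37, 17, 10, 64, 29, 17, and the totals with 34, 18, 12, 74, 34, 20, 128, 58, 34. Name the test used (two-sample t-test).
- State that 100 patients (50 per arm) give about 70% power for 20 µm with SD 40 µm at two-sided 5%, or 80% power for about 22.6 µm. Note that this is for an unadjusted t-test and that baseline adjustment may raise it by an unquantified amount.
- State whether SD 40 µm is an unadjusted or a baseline-adjusted SD.
- Use one total, 100 or 102, in the synopsis and in sections 3.3 and 7.7.

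The cost is protocol wording and table values only. No additional patients and no change to the analysis are required. The one downside is a less favourable stated power.

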## **8. INFORMED CONSENT, DATA PROTECTION, TRIAL RECORDS**

The trial will be carried out in compliance with the protocol, the ethical principles laid down in the Declaration of Helsinki, in accordance with the ICH Harmonized Tripartite Guideline for Good Clinical Practice (GCP), relevant BI Standard Operating Procedures (SOPs) and relevant regulations.

Standard medical care (prophylactic, diagnostic and therapeutic procedures) remains in the responsibility of the treating physician of the patient.

The Investigator will inform the Sponsor immediately of any urgent safety measures taken to protect the trial subjects against any immediate hazard, and also of any serious breaches of the protocol or of ICH GCP.

The rights of the Investigator and of the Sponsor with regard to publication of the results of this trial are described in the Investigator contract. As a rule, no trial results should be published prior to finalization of the Clinical Trial Report.

The certificate of insurance cover is made available to the Investigator and the patients, and is stored in the ISF.

### **8.1 TRIAL APPROVAL, PATIENT INFORMATION, AND INFORMED CONSENT**

This trial will be initiated only after all required legal documentation has been reviewed and approved by the respective Institutional Review Board (IRB) / Independent Ethics Committee (IEC) and competent authority (CA) according to national and international regulations. The same applies for the implementation of changes introduced by amendments.

Prior to patient participation in the trial, written informed consent must be obtained from each patient (or the patient's legally accepted representative) according to ICH / GCP and to the regulatory and legal requirements of the participating country. Each signature must be personally dated by each signatory and the informed consent and any additional patient information form retained by the Investigator as part of the trial records. A signed copy of the informed consent and any additional patient information must be given to each patient or the patient's legally accepted representative.

Re-consenting may become necessary when new relevant information becomes available and should be conducted according to the sponsor's instructions.

### **8.2 DATA QUALITY ASSURANCE**

A quality assurance audit/inspection of this trial may be conducted by the Sponsor, Sponsor's designees, or by IRB / IEC or by regulatory authorities. The quality assurance auditor will have access to all medical records, the Investigator's trial-related files and correspondence, and the informed consent documentation of this clinical trial.

### 8.3 RECORDS

Electronic Case Report Forms (eCRF) for individual patients will be provided by the Sponsor. [See Section 4.1.5.2](#) for rules about emergency code breaks. For drug accountability, refer to [Section 4.1.8](#).

#### 8.3.1 Source documents

In accordance with regulatory requirements the Investigator should prepare and maintain adequate and accurate source documents and trial records that include all observations and other data pertinent to the investigation on each trial subject. Source data as well as reported data should follow good documentation practices and be attributable, legible, contemporaneous, original and accurate. Changes to the data should be traceable (audit trail). Data reported on the CRF must be consistent with the source data or the discrepancies must be explained.

The current medical history of the subject may not be sufficient to confirm eligibility for the trial and the Investigator may need to request previous medical histories and evidence of any diagnostic tests. In this case the Investigator must make three documented attempts to retrieve previous medical records. If this fails a verbal history from the patient, documented in their medical records, would be acceptable.

#### 8.3.2 Direct access to source data and documents

The sponsor will monitor the conduct of the trial by regular on-site monitoring visits and in-house data quality review. The frequency of on-site monitoring will be determined by assessing all characteristics of the trial, including its nature, objective, methodology and the degree of any deviations of the intervention from normal clinical practice.

The Investigator /institution will allow on-site trial-related monitoring, audits, IRB / IEC review and regulatory inspections. Direct access must be provided to the CRF and all source documents/data, including progress notes, copies of laboratory and medical test results, which must be available at all times for review by the CRA, auditor and regulatory inspector (e.g. FDA). The CRA and auditor may review all CRFs and informed consents. The accuracy of the data will be verified by direct comparison with the source documents described in [Section 8.3.1](#). The sponsor will also monitor compliance with the protocol and ICH GCP.

#### 8.3.3 Storage period of records

Trial sites: The trial sites must retain the source and essential documents (including ISF) according to the national or local requirements (whatever is longer) valid at the time of the end of the trial.

Sponsor: The sponsor must retain the essential documents according to the sponsor's SOPs.

### 8.4 EXPEDITED REPORTING OF ADVERSE EVENTS

BI is responsible to fulfil their legal regulatory reporting obligation and in accordance to the requirements defined in this CTP.

## 8.5 STATEMENT OF CONFIDENTIALITY AND PATIENT PRIVACY

Individual patient data obtained as a result of this trial is considered confidential and disclosure to third parties is prohibited with the exceptions noted below. Patient privacy will be ensured by using patient identification code numbers.

Data protection and data security measures are implemented for the collection, storage and processing of patient data in accordance with the principles 6 and 12 of the WHO GCP handbook.

Treatment data may be given to the patient's personal physician or to other appropriate medical personnel responsible for the patient's welfare. Data generated as a result of the trial need to be available for inspection on request by the participating physicians, the sponsor's representatives, by the IRB / IEC and the regulatory authorities.

### 8.5.1 Collection, storage and future use of biological samples and corresponding data

Measures are in place to comply with the applicable rules for the collection, storage and future use of biological samples from clinical trial participants and the corresponding data, in particular

- A Quality Management System has been implemented to ensure the adherence with the Principles of Good Clinical Practice as outlined in 'Note For Guidance On Good Clinical Practice' (CPMP/ICH/13 5/95)
- The BI-internal facilities storing and analyzing biological samples and data from clinical trial participants as well as the laboratories' activities for clinical trials sponsored by Boehringer Ingelheim are regularly audited. The analytical groups and the banking facility are therefore assessed to be qualified for the storage and use of biological samples and data collected in clinical trials.
- Samples and data are used only if an appropriate informed consent is available.

